3.4. Statistical analysis

3.4.1. Preliminary considerations

All statistical analyses will be performed using SAS v. 9.2. Basic summary statistics will be calculated for all outcome variables and covariates of interest. Continuous variables will be checked for normality using Q-Q plots.

3.4.1.1. Missing data. Analyses will use an intent-to-treat approach that includes all patients randomized. Study procedures have been proposed to minimize loss of data due to withdrawal or loss. However, sensitivity analyses will be employed to assess the impact of missingness and both conservative and liberal imputations will be used.

3.4.1.2. Adjustment for Clustering. Clusters exist within the intervention arm and analyses thus require consideration of the effects due to clustering, assessed by analyzing within- and between-cluster variance as well as estimating the intraclass correlation coefficient using generalized linear mixed effects modeling. The cluster effect will be deemed significant if the appropriate covariance parameter estimate obtained from the model has p -value <0.05 .¹⁴² In this event, rather than using a two-sample, two-sided, z-test to compare proportions between the two treatment arms and the t-test (or the Mann-Whitney test if distributions are sufficiently non-normal) for the comparison of means, the cluster-adjusted chi-square test will be used to compare proportions and the cluster-adjusted t-test (or the cluster-adjusted Wilcoxon Rank-Sum test if distributions are sufficiently non-normal) will be used to compare means. Similarly, rather than using linear regression analysis to analyze relationships between continuous dependent variables and indicated covariates, linear mixed modeling will be employed. Lastly, rather than using logistic regression analysis to assess relationships between dichotomous dependent variables and indicated covariates, generalized linear mixed effects modeling will be employed.

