3.4.2. Data Analysis

Primary Aim 1. In a randomized design, determine the efficacy of the 12-month ELM Intervention, relative to Education Control, in an ethnically diverse sample of MetS patients. We hypothesize that the ELM intervention will produce a clinically significant remission of the MetS in at least 40% of those treated, while the remission rate in the Enhanced Usual Care Arm will not be higher than 15% at 12 months.

For each arm, the proportion of patients in remission of MetS at 12 months will be computed. The appropriate 2-sample test (see 'Adjustment for Clustering' section) will be used to compare the proportions. We will also test the hypothesis that the intervention produces a 12-month MetS remission rate of $\geq 40\%$.

Identification of a clinically significant primary endpoint and threshold on that endpoint is crucial to the determination of whether or not a proposed treatment deserves further testing.¹⁰⁴ The dichotomous rate of MetS remission (i.e., no longer meeting criteria) is the most popular primary endpoint in clinical trials of the MetS.^{92-94, 105-107} A continuous MetS score has not been validated in American adults.^{108, 109}

Secondary Aim 2. To assess the sustainability of the combined ELM plus Extended Maintenance Intervention on remission of the MetS at 24 months. We hypothesize that the ELM intervention will produce a clinically significant remission of the MetS in at least 38% of those treated, while the remission rate in the Education Control arm will not be higher than 15%.

Analytic procedures will be exactly the same as those for the Primary Aim (above).

Secondary Aim 3. To assess the impact of the 12-month ELM Intervention, and the 24-month ELM plus Extended Maintenance Intervention, on intermediate behavioral outcomes (dietary intake, physical inactivity, and stress) and secondary outcomes (body mass index, vitality, and MetS components).

Separate analyses will be conducted for each outcome. Mean changes (from baseline to 12 or 24 months) between the two arms will be compared using the appropriate 2-sample test (see 'Adjustment for Clustering'). The dependent variable will be the respective outcome at 12 or 24 months and the covariate predictors will be the baseline value and treatment allocation.

Exploratory Aim 4. To develop a system for monitoring costs of the intervention and of medical care over 24 months of follow up in all randomized patients.

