Cost and resource use information will be collected in all patients for the interventions (e.g., time cost for the interventions, productivity loss, enrollment in other wellness programs) and for their health care. Candidate program costs include fixed and variable costs of the ELM Intervention and Education Control. These costs

include the ELM Coach and Coach Assistant time spent delivering the program, time spent training and preparing for each group session and time spent making calls to patients between group sessions, valued at these positions' average hourly wage, group meeting costs (e.g., meeting room space, meals), printed materials, and pedometers. Candidate patient costs include the patient's time spent attending the group sessions, travel time between home and the group sessions, and productivity losses to due absenteeism and presenteeism (measured using the Work Productivity and Activity Impairment Questionnaire),¹³³ valued at the average wage adjusted for socio-demographic characteristics. Health care and wellness-related costs include the cost of primary care physician visits, emergency department visits, hospitalizations and other health and wellness provider visits.³⁴ In addition, the cost of participation in other wellness programs will be included, since ELM may be perceived as a substitute for other wellness programs that patients would otherwise engage in. Feasibility and accuracy of all data collected will be determined and a protocol for assessing costs will be developed.

Exploratory Aim 5. *To explore the impact of the ELM intervention at 12 and 24 months on selected biomarkers of CVD (hemoglobin A_{1c}, C-reactive protein, lipoprotein particle composition) and change in the social network.*

Analyses will be approached in the same way as the continuous variables outlined in Secondary Aim 3 above. Change in the social network will focus on: (1) network size; (2) frequency of contacts; and (3) overall social connectedness. We will consider use of analysis of variance with quintiles of social network summary scores¹⁴³ to identify network variables are related to MetS remission. In addition, we will specifically assess the number and frequency of contacts with other ELM participants.

Exploratory Aim 6. *To explore the acceptability of the intervention assessed as the screening to enrollment ratio, the dropout rate within each arm, and the perceived credibility of each arm.*

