3.4.3. Sample Size and Power

The **primary outcome** of the study is remission of MetS from baseline to the 12-month visit. We hypothesize that at least 40% of patients in the Intervention Arm, and no more than 15% in the control arm will achieve remission. This hypothesis is supported by the ELM proof-of-concept study and published data on 12- and 24-month MetS remission rates of 9-14% in both control groups' patients.^{93, 95, 106} The proposed study employs clusters within the treatment arm only. To estimate sample size, adjustments were made for the intra-class correlation coefficient (ICC). Using data from the ELM proof-of-concept study, we conservatively estimate the ICC to be

A two-sample, two-sided, z-test for proportions will be used to compare the rate of MetS remission between the two treatment arms with an overall significance level of 0.05.

The sample size chosen is 48 patients (16/arm). Required sample sizes were computed under several plausible scenarios, indicated by our proof-of-concept study and other relevant studies. Power was set at 80%, alpha was 0.05, and a 20% dropout rate was assumed. **Figure 5** shows that if a sample size of 48 is chosen, there will be adequate power to detect a statistical difference between a remission rate as low as 40% in ELM Intervention arm and as high as 15% in the Education Control arm. Similar sample sizes resulted when the number of participating sites, clusters per site, and patients per cluster (between 10 and 13) were varied. There will be inadequate power to detect an effect if the ELM Intervention effect erodes to below a 38% remission and the Education Control remission rate is as high as

15%. However, this state of affairs would suggest that more developmental work on either the treatment or control group is needed before progressing.

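### The 24-month analyses of continuous outcomes in Aims 3 and 5 make no use of 12-month values from patients who leave later, and the main analysis has no stated rule for missing visits

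*SAP*

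**What the plan says.** SAP section 3.4.2, Secondary Aim 3, gives two methods for the behavioral and secondary outcomes. The first is a two-sample comparison: "Mean changes (from baseline to 12 or 24 months) between the two arms will be compared using the appropriate 2-sample test". The second is a model: "The dependent variable will be the respective outcome at 12 or 24 months and the covariate predictors will be the baseline value and treatment allocation". Both are adopted by Exploratory Aim 5 (biomarkers and social network) as well: "Analyses will be approached in the same way as the continuous variables outlined in Secondary Aim 3 above".

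On missing data, section 3.4.1.1 says "Analyses will use an intent-to-treat approach that includes all patients randomized", and then that "sensitivity analyses will be employed to assess the impact of missingness and both conservative and liberal imputations will be used". It does not define the imputations or tie them to the main analysis of any aim.

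The only mixed model for continuous outcomes is in section 3.4.1.2, and it applies only if the cluster effect reaches p<0.05: "rather than using linear regression analysis to analyze relationships between continuous dependent variables and indicated covariates, linear mixed modeling will be employed". It deals with treatment groups in the ELM arm and is not described as a model for repeated visits.

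**The concern.** Neither Aim 3 method has a visit term, and the 24-month analysis has no place for the 12-month value. Consider a patient who attends at 12 months and withdraws before 24 months. The SAP says this patient is included, but the methods it names need a 24-month value, and no rule supplies one in the main analysis. The 12-month value is in hand and is informative about the missing one, yet it goes unused.

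What is at stake is how the 24-month results on body mass index, vitality, behavior, MetS components and biomarkers are read. If the patients who leave after month 12 differ from those who stay, and differ in another way in the other arm, part of the 24-month difference reflects who stayed rather than what was maintained. The arms differ in structure (groups in the ELM arm only, followed by an extended maintenance phase), and Exploratory Aim 6 treats dropout within each arm as something to be measured. Different reasons for leaving are therefore possible, although the document does not predict them.

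**Working it through.** The SAP gives no numerical figure for Aims 3 or 5, so there is none to reproduce. The check asks how far the stated methods can be off.

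**Inputs from the SAP.** 48 patients in total (section 3.4.3), taken here as 48/2 = 24 per arm. The same sentence prints 16 per arm, a separate inconsistency on which this point does not depend.

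**Assumed inputs.** The SAP gives no SD, between-visit correlation, effect size, or withdrawal rate or mechanism for months 12 to 24. Assumed: SD 1; true difference 0.50 SD at 24 months; 10% or 20% lost after month 12. Two sets of correlations:
- Set A: baseline to follow-up 0.6, 12 to 24 months 0.7; 24 per arm; ELM leavers weighted to poor 12-month change, control leavers random.
- Set B: all correlations equal, at 0.5 or 0.7; withdrawal log-odds change by 1.5 per SD of 12-month change; 600,000 simulated patients per setting.

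**Why bias arises.** Suppose loss depends only on baseline, arm and the 12-month value. Then

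bias of 24-month regression = g × (D_stay − D_all),

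where g is the slope of the 24-month value on the 12-month value given baseline and arm, and D is the baseline-adjusted arm difference at 12 months, among those who stay and among everyone. If selection shifts both arms equally, D_stay = D_all and the bias is zero.

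**Simulated 24-month estimates, true value 0.50** (set B shown as correlation 0.5 / 0.7)

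| Loss after month 12 | Change-score test | Baseline-adjusted regression | Estimate also using 12-month values |
|---|---|---|---|
| B, 20%, random | 0.50 / 0.50 | 0.50 / 0.50 | 0.50 / 0.50 |
| B, 10%, same response rule in both arms | 0.47 / 0.48 | 0.48 / 0.49 | 0.50 / 0.50 |
| B, 20%, same response rule in both arms | 0.45 / 0.47 | 0.47 / 0.48 | 0.50 / 0.50 |
| B, 10%, response-driven in ELM only | 0.56 / 0.54 | 0.53 / 0.53 | 0.50 / 0.50 |
| B, 20%, response-driven in ELM only | 0.61 / 0.58 | 0.56 / 0.56 | 0.50 / 0.50 |
| A, 10%, response-driven in ELM only | 0.55 | 0.53 | 0.50 |
| A, 20%, response-driven in ELM only | 0.64 | 0.60 | 0.51 |

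A repeat of the last row gave 0.63, 0.59 and 0.50.

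**Cross-check of the two sets.** With all correlations 0.6, g = 0.6/(1 + 0.6) = 0.375, and ELM-only loss of 20% gave 0.556, a bias of 0.056. So D_stay − D_all = 0.056/0.375 = 0.149. Set A has the same baseline to 12-month correlation but g = (0.7 − 0.6 × 0.6)/(1 − 0.6 × 0.6) = 0.34/0.64 = 0.531. The same selection then gives 0.531 × 0.149 = 0.08. At 10% loss the bias is about 0.03, so the shift is 0.03/0.375 = 0.08, and set A would give 0.531 × 0.08 = 0.04. The regression bias is thus about 0.03 to 0.04 SD at 10% and 0.06 to 0.10 SD at 20%, depending on the correlations and on how strong the selection is.

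**No true effect, 20% loss.** Regression shows 0.07 (correlations 0.6) to 0.09 (set A) when loss is response-driven in ELM only, and 0.00 when the rule is the same in both arms.

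**Precision.** At 48 patients with 20% loss (0.8 × 48 = 38.4 remaining), the standard error was 0.266 for regression and 0.265 for the estimate using 12-month values. Under purely random withdrawal the gain in set A was 2 to 4%. The bias of 0.056 is 0.056/0.266 = 0.21 of a standard error.

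**Would simple imputation repair it?** With a true 0.50, correlations 0.6 and 20% loss, carrying the 12-month value forward gave 0.43 to 0.52 and carrying baseline forward 0.40 to 0.48. Neither reliably recovers the true value.

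**The case against.** Four stronger readings are tempting, and the document supports none of them.

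- **That the SAP drops patients who miss a visit.** It states no such rule. It says all randomized patients are included and that imputations will be used. Once values are imputed, a change test or regression can include everyone, and some imputations would use the 12-month value. What remains is that the imputations are undefined and appear only with sensitivity analyses.
- **That bias follows whenever withdrawal tracks 12-month response.** It does not. The selection must differ between arms. With the same rule in both arms the regression gave 0.47 to 0.49 on a true 0.50, and exactly equal selection gives none.
- **That the 24-month benefit will be overstated.** The direction depends on the mechanism. A common rule slightly understates it. Nothing in the document says that poor responders leave, or that they do so more in the ELM arm.
- **That 20% will be lost after month 12.** Section 3.4.3 says "a 20% dropout rate was assumed", but for the sample size of the 12-month primary outcome. It is not a rate for months 12 to 24, which is why 10% is shown as well.

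It is also fair to say that visit-by-visit regression adjusted for baseline is conventional, that the aims are secondary and exploratory, and that the gain in precision is slight. All of that stands, and it limits how much weight the point deserves.

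**Conclusion.** The point holds as a gap in the main analysis of the continuous outcomes in Aims 3 and 5. The SAP fixes single-visit methods, promises to include everyone, and states no means of doing so. Data already collected at 12 months are left out of the 24-month estimate.

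The bias in baseline-adjusted regression is about 0.03 to 0.04 SD at 10% loss after month 12 and 0.06 to 0.10 SD at 20%. It is larger for the change-score test: 0.04 to 0.06 SD and 0.08 to 0.14 SD. These figures hold only for response-driven loss confined to the ELM arm, a true effect of 0.50 SD and the assumed correlations. They are well below one standard error in a trial of 48. The reason to act is that the risk can be reduced at little cost, not that a large distortion has been shown. The primary comparison of remission proportions is outside this point.

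**What to change.** For each continuous outcome in Aims 3 and 5, make the main analysis one repeated-measures mixed model of the 12- and 24-month values. Its terms are baseline value, arm, visit and arm-by-visit, an unstructured within-patient covariance (three parameters for two visits), and a group effect in the ELM arm. Read the 12- and 24-month arm differences from this model. Keep the change-score or regression analysis of each visit as a sensitivity check. Define the imputations of section 3.4.1.1 in words that can be programmed, and label them as sensitivity analyses.

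The cost is SAP wording and a few lines of SAS, with no new data. There are three limits to state. The model assumes data are missing at random given the observed visits. It still omits patients with no follow-up visit, so it does not by itself deliver the promise to include everyone randomized, and the imputations are needed for those patients. Clearly non-normal outcomes, for which the SAP now falls back on rank tests, may need a transformation. With 48 patients, it would also be prudent to name in advance a simpler covariance structure in case the model does not converge.

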The DMC will keep records of screened, enrolled, and drop-out rates. Mean differences in credibility between the 2 arms will be assessed in the same way as the continuous variables outlined in Secondary Aim 3 above.

Exploratory Aim 7. *To explore the moderating effects of built and food environment on MetS remission in the ELM Intervention and Control arms at 12 and 24 months.*

[figure not shown]
Moderating effects will be tested using logistic regression analysis (see 'Adjustment for Clustering' section above) with the dependent variable of MetS remission and the covariates of treatment arm, moderator, and the treatment-by-moderator interaction term.

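### Exploratory Aim 5 names only ANOVA on quintiles, with no arm term, to relate network scores to remission; the uncut score plus arm is a cheap improvement

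*SAP*

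**What the plan says.** SAP 3.4.2, Exploratory Aim 5, asks whether ELM changes biomarkers and the social network at 12 and 24 months. It lists three network measures: "Change in the social network will focus on: (1) network size; (2) frequency of contacts; and (3) overall social connectedness". It then says "We will consider use of analysis of variance with quintiles of social network summary" scores, "to identify network variables are related to MetS remission". It adds that "we will specifically assess the number and frequency of contacts with other ELM participants".

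The same section calls remission dichotomous. For Exploratory Aim 7, which also relates a covariate to remission, it specifies logistic regression "with the dependent variable of MetS remission and the covariates of treatment arm, moderator" and their interaction. SAP 3.4.1.2 (Adjustment for Clustering) mentions "logistic regression analysis to assess relationships between dichotomous dependent variables and indicated covariates" as the default that a generalized linear mixed model replaces when the cluster effect is significant.

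The Aim 5 sentence does not say which variable is the factor and which the response, whether arm is in the model, whether the network score is baseline, follow-up or change, or whether remission is at 12 or 24 months.

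**The concern.** Two features of the named method are weak for its question.

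- **Cutting the score.** Fifths discard information within each group. If quintiles are an unordered factor, the test also spends four degrees of freedom on what is most naturally a question of trend. In a small trial each fifth holds few patients and very few remissions.
- **No arm term named.** ELM is expected to raise remission, and the same aim asks whether it changes the network. Arm may therefore be linked to both variables. An analysis without arm cannot separate a network-remission relation from ELM acting on each.

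What is at stake is the yield of a hypothesis-generating analysis: a moderate trend missed, or an arm effect read as a network effect. No confirmatory claim depends on it.

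**Working it through.** **The plan's own figure.** The SAP states no power for Aim 5, so there is none to reproduce. The only size given (SAP 3.4.3) is 48 patients and, in the same sentence, 16 per arm, which for two arms is 2 × 16 = 32. Nor does 48 in total follow from the stated inputs (40% against 15%, two-sided 0.05, 80% power, 20% dropout). The pooled z-test needs

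n per arm = [1.96·√(2 × 0.275 × 0.725) + 0.842·√(0.40 × 0.60 + 0.15 × 0.85)]² / 0.25² = 48.9, so 49.

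That is 98 evaluable, or 98/0.8 = 122.5, so 123 randomised. N is therefore an assumption here: 32 (2 × 16), 38 (48 less 20%), 48, and 96 (2 × 48) as a contrast.

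**Group sizes.** 32/5 = 6.4; 38/5 = 7.6; 48/5 = 9.6. At 27.5% overall remission with equal arms, a fifth holds 6.4 × 0.275 = 1.8 to 9.6 × 0.275 = 2.6 remissions. Expected remissions at 48: 24 × 0.40 + 24 × 0.15 = 13.2, or 13.2 × 0.8 = 10.6 after dropout.

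**Simulation model (assumed).** Score z standard normal within arm; equal arms; logit P(remission) = a_arm + log(OR)·z, with intercepts solved so that remission is 40% (ELM) and 15% (control). Tests at two-sided 0.05, 3,000 to 4,000 trials per cell. Clustering was not simulated.

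**Reading A: quintiles as the factor, four degrees of freedom.** Power at OR 2.5 per SD:

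| Analysis | n = 38 | n = 48 |
|---|---|---|
| Quintile ANOVA, no arm | 29% | 39% |
| Quintile ANOVA plus arm | 31% | 41% |
| Linear trend over quintile number plus arm | 50% | 63% |
| Uncut score plus arm, linear model | 55% | 67% |

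- Total loss: 55 − 29 = 26 and 67 − 39 = 28 points.
- From four degrees of freedom instead of one: 50 − 31 = 19 and 63 − 41 = 22.
- From cutting: 55 − 50 = 5 and 67 − 63 = 4.
- From arm: 31 − 29 = 2 and 41 − 39 = 2.

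Over OR 2 to 3 and n = 32 to 48 the loss is about 15 to 30 points against the uncut score plus arm. Against ordinary logistic regression with a Wald test and the same terms it is 9 to 28. At n = 96, against penalised logistic regression, it is 29, 23 and 13 points for OR 2, 2.5 and 3.

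**Reading B: remission as the factor, quintile code 1 to 5 as the response, one degree of freedom.** At OR 2.5, power is 48% (n = 38) and 59% (n = 48), against 56% and 67% for the uncut score plus arm in the same run: a loss of about 8 points. Over OR 2 to 3 and n = 32 to 48 it is about 4 to 10.

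**Weaker effect and other shapes.** At OR 1.5 the loss is about 1 to 9 points across both readings. For Reading A against penalised logistic regression at n = 38 to 48, a step at the top fifth costs 2 to 5 points. For an assumed U-shape (1.2·z² on the logit) the order reverses: quintile ANOVA has 43.3% power against 12.7% at n = 38, and 53.1% against 13.2% at n = 48.

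**Leaving arm out.** With no within-arm network effect and ELM assumed to shift the score by 1 SD, an association appears in about 8 to 9% of trials under Reading A and 12 to 13% under Reading B, against about 5% with arm in the model. At 0.5 SD, Reading A gives 5 to 6.5%. This applies to follow-up or change scores; ELM cannot shift a baseline score.

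**The case against.** The strongest reply is that little is fixed here. The method is only to be considered, in an exploratory aim that specifies no shape, and an omnibus test over fifths is a defensible way to look for any pattern. It is clearly better for a U-shape. That stands, and it is why the point ranks low.

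Four stronger readings are tempting, but the SAP does not support them.

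- *The plan gives up 15 to 30 points of power.* That needs quintiles to be the factor, which the sentence does not say. It also needs an assumed N, effect size and log-linear shape. Under the other variable roles most of the loss disappears.
- *The plan pools the arms.* It is silent. Aim 5 opens by following Secondary Aim 3, where treatment allocation is a covariate. That covariate belongs to models of the continuous outcome, so it does not settle the remission analysis, but pooling is not stated.
- *ANOVA on a yes/no outcome is invalid.* In simulation without any effect, quintile ANOVA rejected in 4.2 to 5.3% of trials at n = 32 to 96.
- *The SAP prescribes logistic regression for every yes/no outcome and Aim 5 breaks that rule.* SAP 3.4.1.2 mentions it only within the clustering adjustment. The firm contrast is with Aim 7.

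The 8 to 13% figure can also be disputed. If ELM shifts the score, the unadjusted association is real in the pooled sample. It misleads only if read as a relation within arms, so the SAP should say which is meant.

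**Conclusion.** A cheap improvement, of low severity. The only method named for relating network scores to remission is weaker for a monotone relation than the uncut score would be, and it names no arm term. This holds under either assignment of variable roles; only the size differs, from a few points to about 30. All power figures rest on the assumed N of 32 to 48, odds ratio per SD, log-linear shape and 40%/15% remission, with clustering ignored. The arm figure rests on an assumed 1 SD shift in a post-baseline score. Nothing in the primary or secondary aims is affected.

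**What to change.** Replace the sentence in Exploratory Aim 5 with: logistic regression of remission on each continuous, standardised network score plus treatment arm, stating whether the score is baseline, follow-up or change and whether remission is at 12 or 24 months. If the cluster test of SAP 3.4.1.2 is significant, use the generalized linear mixed model with the same terms. Penalised likelihood is an option if remissions are few. Report the odds ratio per SD with its confidence interval, labelled exploratory, and the number of remissions beside it. Keep quintiles as a descriptive table or plot of shape.

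Cost: one sentence and no new data. The downside is that a linear term can largely miss a U-shaped relation, so the quintile plot must be shown with the model and any curvature described.
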